#### 9. Safety and Tolerability Analysis

Safety assessments will be performed at scheduled timepoints throughout the study and include physical examination, vital signs, ECGs, standard clinical laboratory testing (serum chemistry, hematology, urinalysis), C-SSRS, prior and concomitant medications (CMs), and AEs.

All safety analyses will be performed on the Safety Population by actual treatment received.

#### 9.1. Adverse Events

Treatment-emergent AEs will be summarized in all AE tables. A TEAE is defined as any AE with an onset date/time on or after the first dose of study drug. All AE summary tables will include the number and percentage of participants with an AE within a category, system organ class (SOC), or preferred term (PT).

An overall summary of the number and percentage of participants with TEAEs will be provided by treatment group. Frequencies and percentages of the following will be included: with any TEAE, participants with any TEAE related to treatment, participants with any TEAE leading to

treatment discontinuation, participants with any serious treatment emergent AE (SAE), participants with any SAE related to treatment, and participants with any TEAE leading to death.

The incidence of TEAEs will be summarized with frequencies and percentages by the following:

- PT in descending order of frequency
- SOC and PT
- SOC, PT, and maximum severity (Mild; Moderate; Severe)
- SOC, PT, and maximum relationship to study drug (Not Related; Related)

Incidences other than the PT summary will be presented alphabetically by SOC and PT. Participants with multiple events within the same SOC and PT will be counted once per SOC and PT. TEAEs with a missing severity will be considered severe and TEAEs with a missing relationship to study drug will be considered related. AEs with a relationship of study drug of possibly or probably related will be considered related.

All AEs will be presented in a listing. AEs that are treatment emergent will be flagged.

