13.2 Adverse Events

13.2.1 Definitions

Adverse Event

An Adverse Event (AE) is any untoward medical occurrence in a participant or clinical investigation participant undergoing a study procedure or administration of a study drug. An AE can therefore be any unfavorable and unintended sign (including an abnormal laboratory finding), symptom, or disease temporally associated with the use of the study drug, whether considered related to the study drug or not.

Related Adverse Event

A related AE is an AE with a causality rating of "possible" or "probable".

Not related Adverse Event

A not related AE is an AE with a causality rating of "unlikely" or "unrelated".

Laboratory Abnormality

A laboratory abnormality is any clinically significant laboratory abnormality suggesting a disease or organ toxicity and which is of a severity requiring active management (i.e., changes of dose, discontinuation of drug, more frequent follow-up, medical treatment or a diagnostic investigation). Laboratory abnormalities are also considered AEs, if clinically significant.

Pretreatment Adverse Events

A pretreatment AE is any AE occurring during the pretreatment period (between informed consent and initiation of a study drug).

Post-study Adverse Event

A post-study AE is an AE occurring up to 30 days after the treatment period.

Treatment-emergent Adverse Events

Treatment-emergent adverse events (TEAEs) are all AEs occurring during the treatment period or a pretreatment AE that worsens in intensity during the treatment period.

Treatment Period

The treatment period is the period during which a participant receives study drug (i.e., first dose through last dose).

Serious Adverse Event

A serious adverse event (SAE) is any untoward medical occurrence that results in death, is life-threatening, requires in-participant hospitalization or prolongation of existing hospitalization, results in persistent or significant disability/incapacity, is a congenital anomaly/birth defect observed in any offspring of the participant conceived during treatment with the study drug or is an important medical event. See Section 14 for more details on SAEs.

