13.2.2.1 Onset Date

The onset date is the date when the first sign(s) or symptom(s) were first noted. For example, if the AE is an abnormal laboratory test (such as "platelets low"), the onset date is the date when the sample was taken. If the participant was hospitalized for meningitis, and symptoms such as fever, headache and nausea started the day before the hospitalization, the onset date is the day symptoms presented versus day of hospitalization.

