13.2.2.2 Assessment of Intensity

The intensity of each AE will be rated according to the following 3-point scale:

- Mild: Awareness of signs or symptoms, but no disruption of usual activity.
- Moderate: Event sufficient to affect usual activity (disturbing).
- Severe: Inability to work or perform usual activities (unacceptable).

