	9.4.	Electrocardiograms	. 33
	9.5.	Physical Examination.	. 33
	9.6.	Columbia Suicide Severity Rating Scale (C-SSRS)	. 34
	9.7.	Prior and Concomitant Medications	. 35
10.	Ch	anges from Planned Analysis	. 35
11.	Otl	ner Planned Analysis	. 36
	11.1.	Pharmacokinetic and Pharmacodynamic Analysis	. 36
12	Do	forances	27

This statistical analysis plan (SAP) describes the planned analysis and reporting for Cognition Therapeutics, Inc. protocol number COG0201 (A Randomized, Double-Blind, Placebo-Controlled, Parallel-Group, Phase 2 Study to Evaluate the Safety and Efficacy of CT1812 in Participants with Mild to Moderate Alzheimer's Disease), Version 6.0, dated 13-Jun-2023. Reference materials for this statistical plan include the protocol and the accompanying sample data collection documents. Operational aspects related to collection and timing of planned clinical assessments are not repeated in this SAP unless relevant to the planned analysis.

The structure and content of this SAP provides sufficient detail to meet the requirements identified by the Food and Drug Administration (FDA), European Medicines Agency (EMA), and International Conference on Harmonization (ICH) of Technical Requirements for Registration of Pharmaceuticals for Human Use: Guidance on Statistical Principles in Clinical Trials. All work planned and reported for this SAP will follow internationally accepted guidelines, published by the American Statistical Association and the Royal Statistical Society for statistical practice.

The planned analyses identified in this SAP may be included in clinical study reports (CSRs), regulatory submissions, or future manuscripts. Also, post-hoc exploratory analyses not necessarily identified in this SAP may be performed to further examine study data. Any post-hoc or unplanned, exploratory analysis performed will be clearly identified as such in the final CSR.

The statistical plan described hereafter is an *a priori* plan. It will be submitted to file prior to any unblinded inferential or descriptive analysis of data pertaining to Cognition Therapeutics, Inc.'s study COG0201.

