#### 6.1.8. Derived Variables

- Change from baseline = value at current time point value at baseline.
- Treatment-emergent AE (TEAE) = any AE with an onset date/time on or after the first dose of study drug.
- Modified Hachinski total score = the sum of the individual 8 item scores. Items 1, 6, 7 & 8 attract a score of 2-points if present (range of 0-8). Items 2, 3, 4 & 5 attract a score of 1-point if present (range of 0-4). The total score ranges from 0 12.
  - The sites were originally responsible for manually calculating the total score and entering it into the clinical study database. To ensure accuracy, it was decided to re-derive this total score in the ADaM dataset.
- ADCS-ADL total score = the sum of the individual 23 item scores. The score ranges from 0-78.
  - The sites were originally responsible for manually calculating the total score and entering it into the clinical study database. To ensure accuracy, it was decided to re-derive this total score in the ADaM dataset
- The ADAS-13 total score = the sum of all 13 individual items (word recall; commands; constructional praxis; delayed word recall; naming objects and fingers; ideational praxis; orientation; word recognition; remembering test instructions; spoken language; word finding; comprehension of spoken language; and number cancellation).
  - The score for the number cancellation item was originally set up to be derived within the clinical study database, however prior to database lock, an error was discovered in the derivation of this item score. This error subsequently impacts

the derivation of the ADAS-13 total score, which was also originally set up to be derived within the clinical study database.

- As a result, both the number cancellation item score and the ADAS-13 total score will be re-derived in the ADaM dataset for analysis purposes as follows:
- The number cancellation score will be derived in two steps:
  - Step 1: Calculate the preliminary number cancellation item score as (number of targets hit) – [(number of errors) + (number of times to remind to task)]
  - Step 2: Take the preliminary number cancellation item score calculated in Step 1 and re-scale as follows:
    - If number cancellation item score is > 30 then re-scale as 0
    - If  $24 \le$  number cancellation item score  $\le 29$  then re-scale as 1
    - If  $18 \le$  number cancellation item score  $\le 23$  then re-scale as 2
    - If 12 < number cancellation item score < 17 then re-scale as 3

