#### 10. Changes from Planned Analysis

Four additional analysis populations are defined in this SAP but are not defined in the study protocol: All Subjects Population, mITT Population, Completers Population, and PK Population. These analysis populations have been added to enable the summary of disposition, the primary analysis of efficacy data (mITT), a sensitivity analysis of efficacy data (Completers), and analysis of PK data (PK). The Per-Protocol Population, also not defined in the study protocol but included in V1.0 of the SAP, was removed.

The score for the number cancellation item was originally set up to be derived within the clinical

study database, however prior to database lock, an error was discovered in the derivation of this item score. This error subsequently impacts the derivation of the ADAS-13 total score, which was also originally set up to be derived within the clinical study database. As a result, both the number cancellation item score and the ADAS-13 total score will be re-derived in the ADaM datasets for analysis purposes.

The Modified Hachinski total score and ADCS-ADL total score were originally calculated and entered into the study database by the sites. To ensure accuracy, it was decided to re-derive these total scores in the ADaM dataset.

Composite z-score scales (Cognitive Composite score; Memory composite score; Attention composite score; Executive Function composite score) are added to efficacy endpoints and their derivation are included in Section 6.1.8.

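### The SAP defines treatment-emergent AEs by onset alone, without the protocol's worsening limb or its last-dose cut-off, and declares neither difference

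*SAP*

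**What the plan says.** Protocol 13.2.1 gives a treatment-emergent AE (TEAE) two limbs. The first is an AE occurring in the treatment period, which runs from first to last dose. The second is "a pretreatment AE that worsens in intensity during the treatment period". The same section fixes the term used there: "A pretreatment AE is any AE occurring during the pretreatment period", meaning between consent and first dose. It treats AEs in the 30 days after treatment as a separate, post-study category.

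The SAP has one limb. Section 6.1.8 defines a TEAE as "any AE with an onset date/time on or after the first dose" of study drug, and Section 9.1 repeats the rule: "A TEAE is defined as any AE with an onset date/time on or after the first dose of study drug". Neither place mentions worsening or sets an end date. Section 9.1 also makes TEAEs the content of every AE table.

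SAP Section 10 sets out departures from the protocol, beginning "Four additional analysis populations are defined in this SAP but are not defined in the study protocol", and goes on to re-derived scores and added composites. The TEAE definition is not among them. The SAP's document history does record a TEAE edit, but it concerns onset on the day of first dose.

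**The concern.** Safety and tolerability are the primary objective, and the incidence and severity of AEs is the first safety endpoint in both documents. Under the SAP's rule, an AE that starts in screening and becomes worse on treatment may not be counted, although the protocol's own definition counts it. As a hypothetical case, take a mild headache after the screening lumbar puncture that becomes moderate in the second week of dosing. The protocol makes it a TEAE. If it stays as one record dated to the puncture, the SAP does not.

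At the other end of the window, the SAP counts AEs that begin after last dose, which the protocol places outside the treatment period. In both respects the tables for the primary objective can differ from what a reader of the protocol would expect, and nothing in the SAP says so.

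**Working it through.** **1. The plan's own figure.** The only numerical statement about AEs is the 91% chance of at least one occurrence at 5% prevalence in 48 participants (Protocol 15.2, SAP 3.2). 1 − 0.95^48 = 0.915, so it reproduces. It is not in dispute.

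**2. The two definitions side by side.**

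| | Protocol 13.2.1 | SAP 6.1.8 and 9.1 |
|---|---|---|
| Onset from first to last dose | counted | counted |
| Onset between consent and first dose, worse on treatment | counted | not counted |
| Onset after last dose | not counted as a TEAE | counted |

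The SAP is narrower in the second row and wider in the third. Section 10 declares neither.

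**3. Does another rule recover the second row?** Protocol 13.2.2.1 dates an AE from its beginning: "The onset date is the date when the first sign(s) or symptom(s) were first noted". Protocol 13.2.2.2 says "The intensity of each AE will be rated according to the following 3-point scale" and gives no rule for a change in intensity. Neither document says that a worsening becomes a new AE record with its own onset. The SAP's Overview says "Reference materials for this statistical plan include the protocol and the accompanying sample data collection documents"; those data collection documents may contain such a rule but are not available here. So an AE kept as one record with a complete pre-dose onset date fails the SAP's test.

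Several provisions limit the loss:
- All AEs are listed (SAP 9.1).
- The listing of AEs leading to drug discontinuation is not confined to TEAEs (SAP 9.1.1).
- Laboratory shift tables do not use the TEAE flag (SAP 9.2.1).
- A partial start date in the month of first dose is generally set to first dose (SAP 6.1.9).

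None of these puts an AE with a complete pre-dose onset date back into the TEAE counts.

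**4. Tables that depend on the flag.** SAP 9.1 has one overall summary and four incidence tables (by PT; by SOC and PT; by maximum severity; by maximum relationship). SAP 9.1.1 has one discontinuation table. 1 + 4 + 1 = 6. SAP 9.1.2 also tabulates SAEs by SOC and PT without saying whether they must be treatment-emergent. It is either a seventh affected table or, if it covers every SAE, a safeguard for the most serious events.

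**5. Are such AEs in the database?** The documents disagree.
- Restrictive: note 27 to Table 1, in both documents, limits screening collection to procedure-related SAEs, and the AE row of both schedules has its first mark at Baseline.
- Inclusive: Protocol 10.2.2 records AEs since Screening before the first dose. Protocol 13.1.1 captures AEs from Visit 1 or consent, and 13.2.2 collects all AEs from consent. Protocol 14.1.2 requires every SAE from consent, whether or not it is procedure-related.

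These cannot all be followed. Under the restrictive reading the worsening limb has almost nothing to act on; under the inclusive reading it may have real data.

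**6. Size per participant.** At the planned numbers, one omitted participant lowers a row's incidence by 1/48 = 2.1 percentage points in one arm, or 1/96 = 1.0 point in the pooled CT1812 group. This holds only if that participant has no other TEAE counted in the row, because SAP 9.1 counts each participant once per SOC and PT. Otherwise the incidence does not change.

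**The case against.** The strongest reply is that no harm has been shown. Four things must coincide: onset between consent and first dose, collection despite note 27, worsening on treatment, and no new record for the worsening. The last depends on documents not seen. The SAP is also consistent with itself, since it repeats note 27 and its schedule starts AE assessment at Baseline. Conditions that predate the start of study procedures are not AEs under Protocol 13.1.1, so the gap covers only the screening window. The protocol defines an AE broadly enough that a worsening might be read as a separate AE. Finally, the protocol's endpoint and its analysis text (15.4) speak of AEs, not TEAEs, and leave detail to the SAP.

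Most of this stands as a limit on size. It does not remove the mismatch. The rule dating onset from the first sign works against reading a worsening as a new AE, and four protocol sections put pre-dose events in the database in spite of note 27. The last argument shows that this is a conflict of definitions and not a changed primary analysis, but the SAP itself chose the TEAE as the unit of its tables.

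A reader might infer three stronger things, none of which the documents support. One is that the tables will understate harm on CT1812; the rule applies equally to placebo. Another is that events will certainly be lost; that depends on record-keeping and collection rules that are missing or contradictory. The third is that the 91% detection figure fails; its arithmetic is correct, and neither document gives a rate of worsening that would change it.

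**Conclusion.** The point holds as an undeclared difference between the SAP's TEAE definition and the protocol's, at both ends of the window. It affects six AE tables, and possibly the SAE tabulation, whose scope is unclear.

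The number of AEs involved cannot be computed from the documents. It is near nil if note 27 governed collection and may be real if the protocol sections on consent-onward collection did. The effect on the worsening side also assumes that a worsening stays within one record under its original onset date. No direction is claimed. The textual mismatch is certain; any effect on the counts is not. It should be fixed because the tables serve the primary objective and the correction is cheap.

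Restoring the worsening limb would not by itself make the definitions agree. They still differ on AEs that begin after last dose until that is aligned or declared.

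**What to change.** - In SAP 6.1.8 and 9.1, add a second limb covering any AE with onset before first dose whose intensity increases during the treatment period. State how an increase is identified: a new AE record or an intensity-change field.
- If neither was captured, a listing cannot show worsening. Have staff blinded to treatment check pre-dose AEs still ongoing at first dose against source records before database lock, or declare in Section 10 that the limb cannot be applied.
- State whether the SAE tabulation in SAP 9.1.2 is limited to TEAEs.
- Either end the TEAE window where the protocol does, or flag AEs with onset after last dose and declare the wider window in Section 10.
- Reconcile note 27 and the AE row of the schedules with Protocol 10.2.2, 13.1.1, 13.2.2 and 14.1.2, and state which pretreatment AEs were collected.

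The cost is some SAP wording and a small derivation change, or a limited source check if intensity changes were not recorded. AE counts may rise slightly.

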15.2 Number of Participants Chosen for This Study

For this trial groups of 48 active-dosed participants per dose level are felt to give adequate sensitivity to detect adverse events. A sample size of 48 active-dosed participants for each dose level (100 mg, 300 mg) has 91% power to detect at least 1 occurrence of any drug-related AE with a true prevalence in the treated population of 5%. Additional participants may be added to replace participants with significant disruption to their visit schedule due to COVID or if there are unanticipated dropouts.

Additionally, for the primary exploratory efficacy analysis relating to the ADAS-COG 11 comparing the combined CT1812 treatment groups versus the placebo group, 48 participants per group provides 81% power to show a treatment difference of 3.0 points assuming a two-sided test at the alpha=0.05 level of significance, a SD of 5.4 points, and a dropout rate of 15%.

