15.4 Data Analysis

All descriptive statistical analyses will be performed using SAS statistical software (Version 9.3 or higher), unless otherwise noted. AEs will be assessed by the investigator for severity and will be coded for summarization using Medical Dictionary for Regulatory Activities (MedDRA® Version 10.1 or higher). Concomitant medications will be coded using WHO Drug Dictionary (enhanced) Format C, 15 Aug 2005 or more recent updated version.

Adverse events will be summarized by Preferred Term and System, for each dose group (including placebo) and the incidence compared. Laboratory measures will be summarized by treatment group and time-point both as absolute values and as change from baseline, with

descriptive statistics summarizing each group and time point. Similar presentation will be used for vital signs and for ECG interval measurements, and changes from pre-treatment baseline.

Additional statistical details will be provided in a prospective statistical plan.

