#### 2. Study Objectives and Endpoints

#### 2.1. Study Objectives

#### 2.1.1. Primary Objective

The primary objective of the study is to:

• To assess the safety and tolerability of CT1812 in participants with mild to moderate Alzheimer's disease (AD).

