#### 2.2. Study Endpoints

#### 2.2.1. Safety Endpoints

The safety endpoints of this study include the following:

- The incidence and severity of adverse events (AEs).
- The change in usage of concomitant medications.
- Changes in vital signs.
- Changes in physical exam findings.
- Changes in electrocardiogram findings.
- Changes in clinical laboratory testing (serum chemistry, hematology, urinalysis).
- Changes in the Columbia Suicide Severity Rating Scale (C-SSRS).

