#### 3.5. Method of Assigning Participants to Treatment Groups

Participants will be randomized in a 1:1:1 ratio to CT1812 100 mg/day, CT1812 300 mg/day or placebo. The placebo will be identical in appearance to the active CT1812. The unblinded statistician assigned to the trial will generate a randomization list with the appropriate number of 4--digit individual study identification numbers (IDs) for each arm, randomly assigned to one of the treatment arms.

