#### 9.4. Electrocardiograms

[figure not shown]
Descriptive summaries will be presented for ECG measures of PR interval (msec), RR interval (msec), QRS interval (msec), QT interval (msec), QTc interval (both Fredericia's and Bazett's correction methods), and HR. These summaries will be presented by visit and treatment group.

The frequency and percentage of participants with normal, clinically significant abnormal, and not clinically significant abnormal ECG results will be summarized for the Safety Population by treatment group and visit.

All ECG results will be listed.

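### SAP 9.4 omits the ECG change from baseline that the protocol promises, without declaring it; a smaller gap is that no drug-minus-placebo estimate is planned for adverse events

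*SAP*

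**What the plan says.** The objective in SAP 2.1.1 is "To assess the safety and tolerability of CT1812 in participants with mild to moderate" Alzheimer's disease.

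**ECG.** Protocol 15.4 first says that laboratory measures are shown as absolute values and as change from baseline, then adds "Similar presentation will be used for vital signs and for ECG interval measurements, and changes from pre-treatment baseline". The synopsis carries the same commitment. SAP 9.4 says "Descriptive summaries will be presented for ECG measures of PR interval (msec"), goes on to the other intervals, QTc by two corrections and heart rate, and adds a by-visit table of normal and abnormal readings. It does not mention change from baseline. SAP 9.2.1 (laboratory) and 9.3 (vital signs) both keep it.

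**Baseline.** SAP 6.1.1 takes the last non-missing observation on or before the first dose. Protocol 10.2.2 puts the Day 1 ECG among the post-dose assessments, at roughly 1–2 hours.

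**Adverse events.** Protocol 15.4 says "Adverse events will be summarized by Preferred Term and System, for each dose group (including placebo) and the incidence compared". The synopsis says only that they are summarised. SAP 9.1 says "The incidence of TEAEs will be summarized with frequencies and percentages by the following", and lists breakdowns by preferred term, organ class, severity and relationship. SAP Section 6 puts 100 mg, 300 mg, pooled CT1812 and placebo in the outputs.

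**Declared departures.** SAP Section 10 lists added populations, re-derived scores and the composite z-scores. It lists nothing on safety.

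**The concern.** A by-visit table of ECG levels mixes differences between people with any effect of treatment. Change from baseline removes the stable part of the between-person difference, and the protocol committed to it. Because the SAP keeps it for laboratory data and vital signs, its absence from 9.4 looks like an oversight. Restoring it without naming the baseline carries a second risk: an algorithm that compares dates only would accept the Day 1 post-dose ECG as baseline.

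For adverse events, the exploratory efficacy endpoints get differences from placebo with 95% intervals (SAP 8.1), while the primary objective gets none. Readers will form the drug-minus-placebo contrast anyway, and the planned tables give them no measure of its uncertainty.

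**Working it through.** **1. The plan's own safety figure.** Protocol 15.2 says 48 per dose level "has 91% power to detect at least 1 occurrence of any drug-related AE with a true prevalence in the treated population of 5"%. Check: 1 - 0.95^48 = 0.915, so it reproduces. It is the chance of at least one event in one active arm and contains no placebo term.

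**2. Which ECG can be the baseline.** ECGs are scheduled at screening and on Days 1, 28, 56, 98 and 182. All except screening are post-dose. The protocol's key to the schedule gives 1–2 hours ± 45 minutes, so even the earliest permitted Day 1 recording falls 60 - 45 = 15 minutes after dosing. Protocol 4.3 reports peak concentration at 1–2 hours and minimal accumulation. Write a participant's untreated level as m, the effect near peak on Day 1 as e1 and on Day 28 as e28:
- baseline = Day 1 post-dose ECG: change = (m + e28) - (m + e1) = e28 - e1
- baseline = screening ECG: change = (m + e28) - m = e28

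If the effect follows concentration and accumulation is minimal, e28 is close to e1, and the first version tends to zero whatever the size of the effect. The screening ECG avoids this.

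**3. Precision of levels and changes.** With equal variances, the variance of change is 2 × SD² × (1 - r), where r is the within-person correlation. It is below the variance of levels when r exceeds 0.5. The documents give neither SD nor r. The half-width for a difference between two arms of 48 is 1.96 × SD × sqrt(2/48) = 0.40 × SD. Assumed QTc values:
- levels, SD 18–22 ms: 7.2–8.8 ms
- changes, SD 12–15 ms: 4.8–6.0 ms

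These SDs imply r from 1 - 15²/(2 × 18²) = 0.65 to 1 - 12²/(2 × 22²) = 0.85. They show how tightly the arms could be contrasted. A table of change by visit would not itself print that contrast.

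**4. Adverse-event differences.** SAP 3.5: "Participants will be randomized in a 1:1:1 ratio to CT1812 100 mg/day, CT1812 300 mg/day or placebo", so up to 48 per arm. The documents give no placebo rate, so the counts are assumptions. The method is Newcombe's score interval. For 5/48 against 2/48:
- proportions 10.4% and 4.2%; difference 3/48 = 6.25 points, shown as 6.3
- Wilson 95% limits: 4.5% to 22.2%, and 1.2% to 14.0%
- lower limit: 6.25 - sqrt((10.42 - 4.53)² + (13.98 - 4.17)²) = 6.25 - 11.44 = -5.2
- upper limit: 6.25 + sqrt((22.17 - 10.42)² + (4.17 - 1.15)²) = 6.25 + 12.13 = 18.4

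| Assumed events | Difference, points | 95% CI |
|---|---|---|
| 5/48 vs 2/48 | 6.3 | -5.2 to 18.4 |
| 10/48 vs 5/48 | 10.4 | -4.4 to 25.1 |
| 5/48 vs 0/48 | 10.4 | 1.0 to 22.2 |
| 10/96 vs 2/48 (pooled) | 6.3 | -4.6 to 14.5 |

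The second and third rows have the same difference, but only one interval excludes zero. Over equal true rates of 5% to 30%, the simple half-width 1.96 × sqrt(2p(1 - p)/48) runs from 8.7 to 18.3 points. A formal test of 10% against 5% would have about 15% power, so estimation suits this design and testing does not.

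**5. Is an interval promised elsewhere?** SAP 4.1 attaches 95% intervals to statistical tests, and Section 9 names no test. It also allows intervals where appropriate, which is discretionary and names no contrast between arms.

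**The case against.** The strongest reply concerns adverse events. Protocol 15.4 names no statistic, interval or test for its comparison, and the synopsis has no such wording. Columns for each dose, pooled drug and placebo are a reasonable descriptive comparison, and anyone can subtract. The sample size was justified by detection within an active arm. Unadjusted intervals on many preferred terms also invite informal testing. All of this stands, so a reader who infers that the SAP removed a promised comparison of adverse events goes further than the text allows.

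Other stronger readings are also unsupported:
- That safety is analysed only as side-by-side percentages. Laboratory data and vital signs get values and changes from baseline, laboratory data and the C-SSRS get shift tables, and ECGs get descriptive values and a normal/abnormal table.
- That the endpoint "The change in usage of concomitant medications" lost its analysis. The synopsis promises only that these medications be summarised and listed, and SAP 9.7 does so.
- That nonclinical data establish an ECG risk. Protocol 4.2.3 gives hERG IC50 values of 26 and 0.6 µM, with the discrepancy unexplained, and no ECG effects in dogs at mean peak levels up to about 4 µM.

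None of this answers the ECG omission. There the protocol wording is specific, and SAP 9.4 and Section 10 are silent.

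**Conclusion.** The ECG point holds on the text alone: change from baseline is promised twice, is absent from SAP 9.4 and is not declared in Section 10. Its numerical benefit depends on variances that the documents do not give. Under the assumed QTc SDs, the half-width of an arm contrast falls from about 7–9 ms to 5–6 ms, and there is a gain only if the within-person correlation exceeds 0.5. The warning about the Day 1 ECG rests on the protocol's own timing. The near-complete cancellation additionally assumes an effect that tracks concentration.

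The adverse-event point is secondary. Section 9 plans no drug-minus-placebo estimate for the primary objective, and at this size the uncertainty is large (6.3 points, -5.2 to 18.4, for the assumed counts). The descriptive tables are valid. What they lack is a stated interval. The figures assume all 48 per arm are dosed.

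**What to change.** **SAP 9.4 (main change).** Add change from baseline for each ECG interval, including Fridericia-corrected QTc, by visit and arm (100 mg, 300 mg, pooled, placebo). Define ECG baseline as the last recording before the first dose, judged by time and not by date, which in practice is the screening ECG. State that the Day 1 ECG is a post-dose observation and cannot serve as baseline under 6.1.1. If the sponsor prefers not to do this, declare the departure in Section 10. One limitation should be stated: the schedule allows screening up to 60 days before Day 1.

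**SAP 9.1 (inexpensive improvement).** Add risk differences from placebo for 100 mg, 300 mg and pooled, with score-type 95% intervals and no p-values, for any TEAE, related TEAE, SAE, TEAE leading to discontinuation, and common preferred terms above a threshold set in advance. A 5% threshold would mean at least 3 of 48, since 0.05 × 48 = 2.4. Label them descriptive and unadjusted for multiplicity.

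**Cost.** A few extra tables from data already collected, with no protocol amendment. The drawback is some risk that unadjusted intervals are over-read, which the label and the short list of categories limit. The text should be settled before unblinding.
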